Magnesium (Mg) is an important intracellular ion with electrophysiological properties. It is essential for optimal metabolic cell function. Mg has proven effective for treating eclampsia, preeclampsia, and torsade's de pointes. Other therapeutic applications such as adjunctive therapy in acute asthma exacerbations, acute coronary syndromes, acute cerebral ischemia, and postoperative pain control are under discussion. (5)

Some studies have shown that serum hypomagnesaemia is common after coronary artery bypass grafts (CABG) and other types of cardiac surgery. (6) and is associated with postoperative morbidity such as atrial tachyarrhythmia.(7)

Some clinical trials have assessed the efficacy of magnesium as a method of intervention to reduce the incidence of postoperative AF.(8)

2. AIM/ OBJECTIVES (Maximum 300 words)

The primary aim of this study is to investigate the anti-arrhythmic effect of Magnesium Sulfate in prevention of atrial fibrillation post cardiac surgery.

3. METHODOLOGY:

Patients and Methods/ Subjects and Methods/ Material and Methods (Maximum 1000 words) *“References may be needed”*

This study is a prospective, randomized controlled trial that will study the postoperative anti-arrhythmic effect of Magnesium Sulfate and clinical outcomes of administration of intravenous Mg Sulfate in patients undergoing open heart surgery.

Randomization will be performed using a computer-generated randomization sequence and allocation concealment to be maintained all through the time of procedure, by using opaque, numbered, and sealed envelopes.

The study protocol will receive ethical approval from the Research Ethical Committee/ Institutional Review Boards, Faculty of Medicine Ain Shams University.

Informed consent will be obtained from each patient before patients' allocation.

Type of the study: prospective randomized clinical trial study protocol.

Study Setting: The operating theaters and ICU of Cardiothoracic institute of Ain Shams University Hospitals.

Study period: one year.

Sample Size:

Using PASS 15 program for sample size calculation, setting power at 80% and alpha error at 0.05, it is estimated that sample size of 65 patients per group (Total 130 patients) can detect an expected medium effect size ($h= 0.50$) for the difference between two groups regarding incidence of post-operative AF using a two-sided z test.

Study population:

Inclusion criteria:

- Age group: Adult patients from age of 18 years to 70 years
- Sex: Both sexes

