Total time of Mg/placebo infusion is 24 hours, and oral tablets for 1 week just before hospital discharge.

Total serum Magnesium level will be measured immediately post weaning of cardiopulmonary bypass, on ICU arrival, after 24 and 48 hours.

Both groups will receive standardized antiarrhythmic medications as per institutional protocols.

Endpoints of the study:

Primary end point:

1. Evaluation of incidence of atrial fibrillation during hospital stay.

Secondary end points:

1. Total ICU stay.
2. Incidence of new postoperative renal impairment
3. Total ventilation time
4. Incidence of readmission with AF during same hospital stay

Ethical considerations:

The study protocol will receive ethical approval from the Research Ethical Committee, Faculty of Medicine Ain Shams University.

Informed consent will be obtained from each patient before patients' allocation.

Statistical Analysis

Based on published meta-analyses reporting AF incidence of 30–40% in controls following cardiac surgery (Cook et al., 2013(11); Klinger et al., 2015(12)) and anticipating a 50% relative risk reduction (RRR) with our optimized Mg protocol (higher bolus dose, post-CPB initiation), we estimated a medium effect size ($h=0.50$). This RRR assumption was derived from:

- Pharmacokinetic data confirming serum Mg levels >2.5 mg/dL reduce AF risk by 45–60% (Fairley et al., 2015(6); Shiga et al., 2004(13))
- Prior positive RCTs using similar high-bolus regimens (2–3g) showing 54–60% RRR (Miller et al., 2005 (14); Kaplan et al., 2003(15))

Using PASS 15, with power=80% and $\alpha=0.05$, a sample size of 65 patients per group (total N=130) provides 85% power to detect an absolute risk reduction of 20% (control:40% , Mg:20%). This aligns with RCTs detecting similar effects in cardiac surgery cohorts (Gu et al., 2012; N=60–100/group (9)). Continuous variables were analyzed using independent t-tests or ANCOVA (adjusted for covariates); non-parametric data employed Mann-Whitney U tests. Categorical outcomes used chi-square or Fisher's exact tests. Multivariable logistic regression adjusted for age, body mass index (BMI), chronic obstructive pulmonary disease (COPD), diabetes status,

ejection fraction (EF), surgery type, and left atrial size (where available). Sensitivity analyses included propensity score matching (PSM) and Bayesian posterior probability estimation.

4. REFERENCES (Maximum 20 references)

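### Post-weaning serum magnesium is measured in every patient and is tied to AF by the plan's own rationale, but it has no place in the AF analysis and its timing relative to study drug is not fixed

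*Combined protocol and SAP*

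**What the plan says.** The background before the Aim gives the rationale: "Some studies have shown that serum hypomagnesaemia is common after coronary artery bypass grafts (CABG) and other types of cardiac surgery". It adds that low magnesium is associated with atrial tachyarrhythmia after surgery.

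The Statistical Analysis section gives two sources for the 50% relative risk reduction. One is a serum threshold: "Pharmacokinetic data confirming serum Mg levels >2.5 mg/dL reduce AF risk by 45–60" (per cent). The other is earlier randomized trials with 2–3 g boluses, reported to show reductions of 54–60%.

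The inclusion and exclusion criteria cover age, type of surgery, ejection fraction, creatinine, urine output, kidney disease and rhythm. None concerns serum magnesium.

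The end of the Anesthetic management section sets the sampling times: "Total serum Magnesium level will be measured immediately post weaning of cardiopulmonary bypass, on ICU arrival, after 24 and 48 hours". The same section starts the infusion after weaning from bypass. Nothing says which comes first, the sample or the infusion.

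The logistic model lists age, BMI, COPD, diabetes, ejection fraction, surgery type and left atrial size, the last only if it has been recorded. Magnesium is not listed. It is not an endpoint, and no subgroup or interaction uses it. The variables for the propensity-score and Bayesian analyses are not given.

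**The concern.** The plan treats serum magnesium as the route to benefit and names a level at which benefit appears. A control patient already above that level might, on this premise, have the lower AF risk without study drug. Eligibility allows such patients, and the plan does not estimate their share.

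The post-weaning level is also the only scheduled magnesium value that could serve as a baseline, since every later one is taken after the infusion has begun. A baseline variable that the rationale links to the outcome is a natural adjustment covariate, and here it costs nothing to obtain. If some samples are drawn after the infusion has started, the value is no longer a baseline in the treated arm, and adjusting for it could remove part of the treatment effect. If its use is chosen only after the data are seen, the analysis is post hoc.

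**Working it through.** **1. The plan's own power figure.** Inputs: 65 per group (Sample Size); "setting power at 80% and alpha error at 0.05"; "using a two-sided z test"; and the statement that this "provides 85% power to detect an absolute risk reduction of 20% (control:40% , Mg:20" (per cent). With the pooled z test:

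- Standard error under no difference: √(2 × 0.30 × 0.70 / 65) = 0.0804.
- Standard error under 40% vs 20%: √((0.24 + 0.16) / 65) = 0.0784.
- Power = Φ((0.20 − 1.96 × 0.0804) / 0.0784) = 70.6%.

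The stated 85% is not reproduced; other two-sided versions of the test give 63.5% to 72.2%. That is a separate issue, but it shows that there is no spare power to absorb a smaller effect.

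**2. What dilution would do, as an assumed illustration.** Let q be the share above 2.5 mg/dL at weaning. The documents do not give q. Assume that these patients have 20% AF risk in both arms and that the rest have 40% vs 20%. Then the control rate is 0.40 − 0.20q and the magnesium rate is 0.20.

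| q | Control rate | Difference | Relative reduction | Power, 65 per arm |
|---|---|---|---|---|
| 0 | 40% | 20 points | 50% | 70.6% |
| 10% | 38% | 18 points | 47% | 62.1% |
| 20% | 36% | 16 points | 44% | 52.9% |
| 30% | 34% | 14 points | 41% | 43.5% |
| 40% | 32% | 12 points | 38% | 34.3% |

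If these patients instead had 40% risk in both arms, power would be 60.4%, 49.8%, 39.5% and 30.2% for q = 10% to 40%.

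**3. What an interaction test could show.** In the first scenario the two strata differ by (0.40 − 0.20) − (0.20 − 0.20) = 0.20. With 65(1 − q) patients per arm below the threshold and 65q above:

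SE = √(0.40 / [65(1 − q)] + 0.32 / [65q])

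- q = 10% (6.5 above per arm): SE = 0.237, power 13%.
- q = 20% (13 per arm): SE = 0.180, power 20%.
- q = 30% (19.5 per arm): SE = 0.159, power 24%.
- q = 40% (26 per arm): SE = 0.150, power 27%.

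On the log-odds scale the range is about 10% to 21%.

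**4. Room in the adjusted model.** Expected events at the planned rates: 65 × 0.40 + 65 × 0.20 = 39. The listed covariates take 8 parameters if surgery type has the three categories in the inclusion criteria, and treatment makes 9: 39 / 9 = 4.3 events per parameter. A tenth would give 3.9. This is why a swap is better than an addition.

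**The case against.** A reader might infer that high-magnesium patients will be enrolled in number and will dilute the contrast. The documents do not support that:

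- No distribution of magnesium is given, and the background says low levels are common after this surgery, so the share may be small.
- The threshold statement does not say that patients already above 2.5 mg/dL gain nothing from more magnesium. A single post-weaning value also does not show that a placebo patient stays above that level throughout the hospital stay.
- The threshold is only one source of the 50% reduction. Nothing says that the earlier trials selected patients on magnesium; if they did not, their effect already averages over such patients.
- The 30–40% control incidence is quoted for cardiac surgery in general. An unselected rate already contains any high-magnesium patients, so lowering it again by 0.20q may count them twice.
- The stated aim is the effect of magnesium sulfate in preventing AF, not the correction of a deficiency. Prophylaxis in all comers is a legitimate question and needs no magnesium criterion.

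A reader might also infer that the post-weaning value would tell an ineffective drug from a diluted effect. With 13% to 27% power for the interaction, it could not do so reliably.

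All of this stands, and it limits the dilution argument to a possibility. It does not answer the narrower point about a collected baseline value with no fixed timing and no planned use.

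**Conclusion.** The point holds in limited form. Three things follow directly from the text: eligibility is open with respect to magnesium; the post-weaning level has no stated analytic use; and its order relative to the infusion is not fixed. The case for adjustment rests on the plan's own link between magnesium and AF. The gain in precision cannot be quantified, because the documents do not give the strength of that link.

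The dilution figures (a difference of 18 to 12 points for 10% to 40% above the threshold) rest on an assumed share, an assumed absence of benefit above the threshold, and a 40% control rate taken to apply only below it. The true dilution could be nil. Any dilution would lower the average effect and the power; it would not bias the randomized comparison or inflate the type I error. Open eligibility is therefore not a defect to correct. The timing and analysis sentences are worth changing.

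**What to change.** Leave eligibility as it is. Before unblinding, add two statements.

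1. **Timing:** the post-weaning magnesium sample is drawn before study drug starts.
2. **Analysis:** that value, kept continuous, is a baseline covariate in the logistic AF model and replaces a listed covariate so that the model does not grow. Left atrial size is the obvious candidate, because it will not be available for everyone.

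A treatment-by-post-weaning-magnesium interaction may be pre-specified, labelled exploratory and reported with its confidence interval. Levels at ICU arrival, 24 hours and 48 hours should not be adjustment covariates in the treatment-effect model, because treatment changes them.

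The cost is two sentences, with no extra patients or tests. The downsides are that one listed covariate is given up, which may itself predict AF, and that the interaction estimate will be imprecise.

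### 65 per group gives about 71% power for 40% versus 20% AF, not the stated 85%, and h = 0.50 is not the effect those rates imply

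*Combined protocol and SAP*

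**What the plan says.** The primary endpoint is the incidence of atrial fibrillation (AF) during the hospital stay. Its sample size is justified in two places in section 3, Methodology, of the combined protocol and SAP.

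- **Sample Size.** The calculation is described as "setting power at 80% and alpha error at 0.05", and it concludes that a "sample size of 65 patients per group (Total 130 patients) can detect an expected medium effect size ($h= 0.50" for "incidence of post-operative AF using a two-sided z test".
- **Statistical Analysis.** The effect size is derived from meta-analyses "reporting AF incidence of 30–40% in controls following cardiac surgery" and from "anticipating a 50% relative risk reduction (RRR) with our optimized Mg protocol". On that basis the plan says "we estimated a medium effect size ($h=0.50". The next sentence repeats the 80% power setting and then states that "65 patients per group (total N=130) provides 85% power to detect an absolute risk reduction of 20% (control:40% , Mg:20" per cent.

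For categorical outcomes the same section names the chi-square or Fisher's exact test.

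**The concern.** The two sections use one sample size, but they treat h = 0.50 and 40% versus 20% as the same effect and attach powers of 80% and 85% to it. Cohen's h is fixed once the two proportions are given, so the equivalence can be checked directly, and so can the 85%.

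This is the only power statement for the primary endpoint. If it is too high, the ethics committee and later readers are told that the trial is much more likely to detect a halving of AF than it is. A reader who trusts 85% would also give a null result more weight as evidence against magnesium than the design supports.

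**Working it through.** **Inputs.** From Sample Size: two-sided z test, alpha 0.05, target power 80%, 65 per group, h = 0.50. From Statistical Analysis: control rate 30–40%, relative risk reduction (RRR) 50%, and 40% versus 20% as the rates in the power claim. Normal quantiles are 1.960 (two-sided 0.05), 0.8416 (80%) and 1.0364 (85%).

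**1. The plan's N from h = 0.50.**

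n = 2 × ((1.960 + 0.8416) / 0.50)² = 62.8, so 63 per group.

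Power at 65 = Φ(0.50 × √(65/2) − 1.960) = Φ(0.890) = 81.3%.

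The 65 per group is therefore consistent with h = 0.50 at 80% power. The 85% is not: at h = 0.50 it needs 71.8, so 72 per group.

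**2. The h implied by the stated rates.**

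h = 2·asin(√p₁) − 2·asin(√p₂)

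- 40% versus 20%: 1.369 − 0.927 = 0.442
- 35% versus 17.5%: 0.403
- 30% versus 15%: 0.364

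At the adopted 50% RRR, no control rate in the plan's range gives 0.50. Solved the other way, h = 0.50 means 17.7% on magnesium from a 40% control rate (RRR 56%), or 10.5% from 30% (RRR 65%).

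**3. Power for 40% versus 20% with 65 per group (pooled z).**

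- Null standard error: √(2 × 0.30 × 0.70 / 65) = 0.0804
- Alternative standard error: √((0.40 × 0.60 + 0.20 × 0.80) / 65) = 0.0784
- Power = Φ((0.20 − 1.960 × 0.0804) / 0.0784) = Φ(0.541) = 70.6%

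**4. Other tests and control rates** (65 per group, two-sided 0.05, RRR 50%; the last two columns are by exact binomial enumeration):

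| Control vs Mg | Pooled z | Arcsine | Unpooled z | Chi-square | Fisher |
|---|---|---|---|---|---|
| 40% vs 20% | 70.6% | 71.2% | 72.2% | 71.6% | 64.1% |
| 35% vs 17.5% | 62.3% | 63.2% | 63.8% | 63.5% | 55.2% |
| 30% vs 15% | 53.6% | 54.6% | 54.8% | 54.2% | 46.1% |

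A one-sided 5% z test, which would contradict the Sample Size section, gives 80.6% to 81.7% for 40% versus 20%, depending on the variant.

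**5. What 40% versus 20% would need (pooled z).**

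n = (1.960·√(2 × 0.30 × 0.70) + z_power·√(0.24 + 0.16))² / 0.20²

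- 80% power: 81.2, so 82 per group
- 85% power: 92.7, so 93 per group

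With 65 per group and a 40% control rate, the magnesium rate would have to be about 17.9% for 80% power and about 16.6% for 85%.

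**The case against.** Five points can be made for the plan.

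- **The Sample Size section is valid by itself.** For h = 0.50, 65 per group does give at least 80%. That stands. The error arises where h = 0.50 is tied to a 50% RRR and to 40% versus 20%.
- **80% and 85% may be target and achieved power.** The two figures could then coexist in one sentence. That is a fair reading, but neither is achieved for 40% versus 20%.
- **The h mismatch does not explain the 85%.** This is correct. The mismatch explains why 65 per group falls below 80% for 40% versus 20%. The 85% is a further error, since h = 0.50 itself gives only 81.3%.
- **The plan also cites reductions of 45–60% and 54–60%.** With a 40% control rate, pooled-z power is 77.9% at 54% RRR and 87.0% at 60%, so h = 0.50 lies within the evidence range the plan quotes. The plan nevertheless adopts 50% and makes its power claim explicitly at 40% versus 20%, so this does not rescue the figure. It could support a restated target if the sponsor justified one.
- **Fisher's test and the 30% control rate are not the plan's stated case.** The sizing test is a z test, and expected event counts (65 × 0.40 = 26 and 65 × 0.20 = 13) would normally lead to chi-square. About 71% is therefore the main figure; 64% and 54% show how far power could fall under a test and a control rate that the plan itself names.

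**Conclusion.** The concern holds. For 40% versus 20% with 65 per group at two-sided 0.05, power is about 71% (70.6% to 72.2% across the z, arcsine and chi-square calculations; 64.1% with Fisher's test), against a stated 85%. The type II error is about 29%, roughly twice the implied 15%. Separately, h = 0.50 does not follow from a 30–40% control rate with a 50% RRR, which gives 0.364 to 0.442.

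Because 40% is the top of the plan's range, about 71% is the most favourable case at 50% RRR; at 30% versus 15% it is about 54%. These figures assume 1:1 allocation, an unadjusted comparison and outcome data on all 130 patients. The documents state no allowance for dropout, and any loss would lower power further.

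**What to change.** In Statistical Analysis, delete the 85% claim and stop presenting h = 0.50 as equivalent to 40% versus 20% or to a 50% RRR. Replacement text could read:

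> With 65 patients per group and a two-sided 0.05 chi-square test, power is about 71% for AF rates of 40% versus 20% and about 54% for 30% versus 15%. Power of 80% is reached at an effect of about h = 0.50, which with a 40% control rate corresponds to about 18% on magnesium.

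Then make the Sample Size section give the same effect, test and power.

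This costs wording only. The stated power becomes less favourable, but no extra patients are needed to correct it. The correction does leave a trial below its own 80% target for 40% versus 20%, so the sponsor should say which course it takes: accept about 71% openly, justify an effect near h = 0.50 as the target, or enlarge the trial to about 82 per group (164 in total, 34 more than planned) before any allowance for dropout.

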- Elective open heart surgeries for coronary bypass grafting CABG, valvular lesion single or multiple replacement, combined CABG and valvular; with EF in preoperative echo is more than or equal 40%

Exclusion criteria:

- Patients refuse to give informed consent.
- Emergency open heart surgeries
- Redo cases.
- Patients with preoperative serum creatinine level ≥ 1.8 mg/dL

- Patients with reduced intra/post operative urine output ≤ 1 ml/kg/hour.
- Patients with Chronic Kidney disease, Renal failure on dialysis
- Patients with rhythm defects as proved by ECG before administration of Mg/Placebo.

Sampling method:

Patients will be randomly allocated by computer generated randomization into two groups A and B:

- **Group A (Study group):** patients receiving Intravenous Mg Sulfate.
- **Group B (Control):** patients receiving Placebo drug.

Anesthetic management:

Full standard preoperative assessment for cardiac surgery will be done for all patients included in the study before planned procedures.

Premedication will be given according to standard protocol in cardiac anesthesia. Routine monitoring included a five-lead electrocardiogram, pulse oximeter and invasive blood pressure. Anesthesia will be induced with midazolam 0.02mg/kg and fentanyl 2-5 microgram /kg and muscle relaxation were achieved cisatracurium 0.15 mg/kg intravenous. After tracheal intubation, central venous line and TEE inserted, then anesthesia will be maintained throughout the procedure with morphin20 microgram/kg /min, cisatracurium 2mg/kg/min and sevoflurane 2%. Ventilation will be adjusted to maintain end-tidal carbon dioxide in the range of 30-40 mmHg.

Then after completion of surgical procedure and successful weaning off Cardiopulmonary bypass the patients will be divided into two groups group A will receive 2 gm of Mg Sulfate diluted in 30 cc normal 0.9 % saline via intravenous infusion over 1 hour (1 Mg sulfate ampoule = 10 cc) and group B will receive 50 cc normal 0.9 % saline via intravenous infusion over same period.

On ICU arrival group A will continue receiving 1 gm of Mg sulfate per hour for five hours via continuous IV infusion, while group B will receive same volume and rate of normal saline.

After 5 hours, group A will receive 200 mg of Mg sulfate per hour for 19 hours via continuous IV infusion, then oral replacement of mag added 1 gm/8 hours tablet, while group B will receive same fluid volume and rate of normal saline followed by oral inert starch tablets.

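### The plan names no single deciding analysis for the primary AF end point and leaves two routes by which randomised patients can fall out of an analysis

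*Combined protocol and SAP*

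**What the plan says.** **Sizing.** The Sample Size section bases 65 patients per group on the "difference between two groups regarding incidence of post-operative AF using a two-sided z test", "setting power at 80% and alpha error at 0.05".

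**Analysis.** Endpoints of the study makes in-hospital AF the only primary end point. The Statistical Analysis section does not mention that end point when it lists its methods. It says "Categorical outcomes used chi-square or Fisher's exact tests", with no criterion for choosing. It goes on: "Multivariable logistic regression adjusted for age, body mass index (BMI", and the covariate list ends with "ejection fraction (EF), surgery type, and left atrial size (where available". The model's outcome is not stated, nor is its standing as primary, secondary or supportive. Only two methods are ranked: "Sensitivity analyses included propensity score matching (PSM) and Bayesian posterior probability estimation".

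**Missing left atrial size.** No rule is given for a patient without the measurement. The Inclusion criteria require a preoperative echo for ejection fraction ("with EF in preoperative echo is more than or equal 40" per cent), but nothing says that left atrial size is recorded from it.

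**Who is analysed.** The Exclusion criteria include "Patients with reduced intra/post operative urine output" at or below a stated threshold. Under Anesthetic management, the two groups are formed and the infusion starts after weaning from bypass. The intraoperative part of the criterion can therefore be known before allocation; the postoperative part cannot. No analysis population is defined.

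**The concern.** Three gaps bear on the same result.

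1. **Deciding analysis.** A chi-square and an adjusted logistic model can disagree on the same data. If the plan does not say beforehand which one counts, a reader of the final report cannot tell whether the choice was made before or after the results were seen.
2. **Left atrial size.** Dropping the patient, dropping the covariate and imputing the value all fit the wording. The first removes randomised patients from the adjusted model. The unadjusted test is not affected.
3. **Postoperative urine output.** An exclusion that takes effect after treatment starts breaks the comparison that randomisation set up. If the treatment influences who meets it, or if those patients differ in AF risk, the remaining groups are no longer comparable. New postoperative renal impairment is a secondary end point, and it is closely related to the excluded condition.

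**Working it through.** **Inputs from the documents.** 65 per arm; two-sided z test with alpha 0.05; 80% power; h = 0.50 (Sample Size). AF 40% on control and 20% on magnesium; control range 30–40% with a 50% relative reduction, hence 30% vs 15% at the lower end (Statistical Analysis).

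**Assumptions, not in the documents.** Moderate covariate effects on the log-odds of AF: age 0.47 per SD, left atrial size 0.4 per SD, valve surgery 0.4, combined surgery 0.9, COPD 0.4, others 0.1. Weak is half of these; strong is about 1.7 to 2 times. Shares: valve 35%, combined 15%, COPD 12%, diabetes 35%. Left atrial size is missing completely at random in 20%.

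**1. The plan's sample size.** n = 2 × ((1.960 + 0.842)/0.50)² = 62.8, so 63 per group against 65 stated. Power at 65 for h = 0.50 is 81.3%. The sample size reproduces.

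**2. The sizing test and the chi-square.** With AF in 26/65 vs 13/65, the pooled rate is 39/130 = 0.30 and z = 0.20/√(0.30 × 0.70 × 2/65) = 2.488. Then z² = 6.190, which is the uncorrected chi-square; p = 0.0128 by both.

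**3. When a small-cell rule would select Fisher.** With equal arms, and AF in fewer than half the patients, the smallest expected cell is total events/2. A value below 5 needs fewer than 10 events among 130. Expected events are 65 × (0.40 + 0.20) = 39, a smallest cell of 19.5; at 30% vs 15% they are 29.25, a cell of 14.6. The chance of falling below 5 at 30% vs 15% is about 1 in a million.

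**4. Two possible deciding analyses, no true effect.** The chi-square errs in 5.2% of trials (exact enumeration at 30% and 40% AF). Simulation gives the extra share in which only the logistic Wald test is significant:

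| Covariate effects | Only logistic significant | Either significant |
|---|---|---|
| none | 1.3–1.5% | 6.5–6.7% |
| weak | 1.6–1.7% | 6.8–6.9% |
| moderate | 2.0–2.2% | 7.2–7.4% |
| strong | 2.6–2.7% | 7.8–7.9% |

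Simulation error is about 0.2 points. In separate null runs the logistic model alone rejected in 5.9–6.1% (error about 0.3 points). It has 9 slopes for the covariates and treatment if surgery has three types, hence 39/9 = 4.3 expected events per slope at 40% vs 20%. At moderate effects, having the choice adds about 7.3 − 5.2 = 2.1 points over the chi-square alone and about 7.3 − 6 = 1.3 over the logistic model alone. At 40% vs 20% the two analyses reach different decisions in 11.0% of trials (7.7% weak, 14.2% strong).

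**5. Left atrial size, adjusted model, 40% vs 20%.** Dropping 20% removes 0.20 × 130 = 26 patients.

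| Covariate effects | Complete data | 20% dropped | Pooled-mean imputation |
|---|---|---|---|
| weak | 71.3% | 60.4% | 71.4% |
| moderate | 73.5% | 63.0% | 73.2% |
| strong | 80.2% | 70.4% | 79.5% |

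The loss from dropping patients is 9.8 to 10.9 points; repeat simulations at moderate effects gave about 9. Omitting the covariate and keeping the patients gave 71.9% against 73.4%, a loss of 1.5 points. Simulation error is 0.6–0.8 points.

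**6. Price of an unadjusted deciding test.** Exact chi-square power at 40% vs 20% is 71.6%. Against the fully observed adjusted model this is 71.3 − 71.6 = −0.3 (weak), 73.5 − 71.6 = 1.9 (moderate) and 80.2 − 71.6 = 8.6 (strong, with simulation error up to 0.8): about 0 to 8 points.

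**7. Urine output.** The documents give no expected share of patients who meet the criterion after allocation, so no figure is offered. The argument rests on the order of events: groups formed and infusion started, then postoperative urine output observed.

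**The case against.** **The chi-square is already in the plan.** This stands. The uncorrected chi-square is the sizing z test, so a reader who infers a conflict between the sizing and analysis sections goes too far. What is missing is the label that makes it decisive.

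**Fisher's test.** A reader might infer that the open choice between chi-square and Fisher costs power, since Fisher has 64.1% at 40% vs 20% against 71.6%. The documents do not support that as an expected harm. The pair is commonly read as Fisher for small expected cells, and step 3 shows that such a rule would almost never select it here. One clarifying line is enough.

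**The false-positive figure.** Nothing in the documents says the better of two results would be reported, and the covariate effects are assumed. Part of the excess over 5% belongs to the logistic Wald test itself. The figure shows what the wording permits; it is not a forecast.

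**Left atrial size.** Two of the three readings cost little. The 10-point loss needs both an assumed 20% missing share and deletion of those patients, and it touches only the adjusted model.

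**Adjusted or unadjusted.** Preferring an unadjusted deciding test is a trade-off, and the adjusted model may have more power. This stands; what matters is that one is named in advance.

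**Urine output.** A reader might infer that the plan commits to deleting these patients from the analysis. It does not say so. It lists the criterion as an exclusion and defines no analysis set, so deletion is what literal application would produce.

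**Timing.** The methods are written in the past tense, so data may already exist. The documents do not settle this.

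**Conclusion.** The point holds as a specification gap worth correcting. The primary AF end point has no named deciding analysis, the logistic model is unranked, and randomised patients can be lost through a post-allocation exclusion and, in the adjusted model only, through missing left atrial size.

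Under the assumed moderate effects, a free choice between chi-square and logistic model gives about 7.3% false positives (roughly 6.5% to 7.9% from no to strong covariate effects), not all of it due to choosing. Dropping an assumed 20% of patients costs about 10 points of adjusted power, against about 1 to 1.5 for omitting the covariate. The bias from the urine-output exclusion is possible but cannot be sized.

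A reader might also blame test choice for the gap between the 71.6% computed here and the 80% and 85% power in the plan. That would be wrong: 40% vs 20% corresponds to h = 0.44 rather than 0.50, which is a separate sizing question.

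**What to change.** Before unblinding, add to the Statistical Analysis section:

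1. **Population.** AF is analysed in all randomised patients in their allocated arm, including those who meet the postoperative urine-output criterion after allocation. This concerns who is analysed, not how they are treated. Rule 3 alone would not secure it.
2. **Deciding test.** Name one, for example the uncorrected chi-square (equal to the sizing z test), with the risk difference and 95% confidence interval. State that Fisher's test replaces it only if an expected cell count is below 5. Label the logistic model supportive, with AF as its outcome.
3. **Left atrial size.** Impute missing values without using arm or outcome, for example with the pooled mean, so that every patient stays in the adjusted model. Where the preoperative echo provides the measurement, record it.

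If outcome data by arm have already been seen, the report should say that these choices were made afterwards.

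**Cost.** A few SAP sentences, one case report form field if left atrial size is collected, and no extra patients. An unadjusted deciding test gives up about 0 to 8 power points against a fully observed adjusted model. If the sponsor prefers the adjusted model as decisive, that can be defended provided it is named in advance, rule 3 applies, and its error rate of about 6% is addressed.
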